### **Everolimus: experience in patients with TSC**

Everolimus is a kinase inhibitor indicated with FDA approval for the treatment of:

- adults with renal angiomyolipoma and TSC, not requiring immediate surgery. The effectiveness of everolimus in the treatment of renal angiomyolipoma is based on an analysis of durable objective responses in patients treated for a median of 8.3 months. Further follow-up of patients is required to determine long-term outcomes.
- pediatric and adult patients with TSC who have subependymal giant cell astrocytoma (SEGA) that requires therapeutic intervention but cannot be curatively resected. The effectiveness is based on demonstration of durable objective response, as evidenced by reduction in SEGA tumor volume. Improvement in disease-related symptoms and overall survival in patients with SEGA and TSC has not been demonstrated.

There is considerable experience with everolimus use in TSC patients. In a prospective, open-label trial of everolimus for SEGAs in 28 patients, everolimus was associated with few serious side effects during the initial 6 months [8]. Self-limited upper respiratory tract infections and stomatitis were most frequent. Four patients had serious adverse events during the 6-month trial but they were not clearly drug related: hospitalization for respiratory infection (n=2; one had a prior history of reactive airway disease; one also had grade 3 vomiting) and convulsion (n=2). Twenty-five of these patients continued on everolimus for an average of 3 years and no new serious adverse events occurred [26]. A Phase III, prospective, double blind, randomized, multi-center study compared everolimus (n=78) and placebo (n=39) in TSC patients with radiologically enlarging SEGAs [27]. Everolimus was given at 4.5 mg/m^2/day and titrated to a level of 5-15 ng/ml; MRI scans were performed at 3, 6, and 12 months after initiating treatment. The investigators found that 27 of 78 patients (34.6%) receiving everolimus, versus none of the placebo group, had a significant response of > 50% reduction in tumor volume (p<0.0001) [27]. Everolimus was generally well tolerated. A subsequent long-term followup study of 28 patients enrolled, 25 were still under treatment at the time of analysis.[28] Median dose was 5.3 mg/m^2/day and median treatment duration was 34.2 months (range 4.7-47.1). At all time points (18, 24, 30, and 36 months), primary SEGA volume was reduced by ≥30% from baseline (treatment response) in 65%-79% of patients. All patients reported ≥1 adverse event (AE), mostly grade 1/2 in severity, consistent with that previously reported, and none led to everolimus discontinuation. The most commonly reported drug-related AEs were upper respiratory infections (85.7%), stomatitis (85.7%), sinusitis (46.4%), and otitis media (35.7%). No drug-related grade 4 or 5 events occurred.[27a] In a larger, international multicenter study, 117 patients were randomly assigned to everolimus (n=78) or placebo (n=39). 27 (35%) patients in the everolimus group had at least 50% reduction in the volume of SEGAs versus none in the placebo group (difference 35%, 95% CI 15-52; p<0.0001).[29] Adverse events were mostly grade 1 or 2; no patients discontinued treatment because of adverse events. The most common adverse events were mouth ulceration (25 [32%] in the everolimus

CONFIDENTIAL

This document and information is the property of the NYU School of Medicine and Langone Medical Center. Do not disclose or use except as authorized in writing by the study IND sponsor

group vs two [5%] in the placebo group), stomatitis (24 [31%] vs eight [21%]), convulsion (18 [23%] vs ten [26%]), and pyrexia (17 [22%] vs six [15%]).[29]

Other studies have used rapamycin to treat angiomyolipomas over 12 months with good efficacy and safety [30]. Everolimus was approved to treat renal angiomyolipomas in TSC. The most common AE during the 48-week trial was stomatitis. The most common Grade 3-4 adverse reactions (incidence >= 2%) were stomatitis, amenorrhea and convulsion. The most common laboratory abnormalities (incidence >= 50%) were hypercholesterolemia, hypertriglyceridemia and anemia. (Novartis data on file. <http://www.pharma.us.novartis.com/product/pi/pdf/afinitor.pdf>. Accessed April 2012)

### **1.5 Dose Rationale and Risk/Benefits**

The starting dose of everolimus for treatment patients will be 4.5 mg/m^2 once daily; adjust to attain trough concentrations of 5-15ng/ml. The dose will be adjusted for co-medications as outlined in section 5.1. However, these are initial doses often need to be titrated up to therapeutic everolimus serum levels (5 – 15 ng/mL). Since our everolimus treatment duration is 7-21 days and the half-life is 30 hours, the time to equilibration will be approximately 150 hours (6.25 days) and will not allow the investigators to adjust dose to achieve therapeutic levels in the initial groups of patients who will be treated for one to two weeks. We will double the dose in our study for patients who are taking an enzyme-inducing antiepileptic drug (EIAED) since serum everolimus levels will be lower due to increased hepatic metabolism.

After a minimum of three patients are treated for one week, if there is no evidence of serious adverse effects and other dose-level tolerability and safety issues, we will extend the treatment duration by a maximum of one week. Again, after a minimum of three patients treated for two weeks without evidence of serious adverse effects and other dose-level tolerability and safety issues, we will extend the treatment duration to three weeks. For patients treated longer than two weeks, an everolimus blood level will be obtained after 10-12 days and used to adjust dose to maintain a serum level of 5-10 ug/ml.

The most common adverse reactions (>30%) to everolimus treatment in TSC patients include stomatitis in patients with angiomyolipomas and stomatitis and respiratory tract infections in patients with SEGAs. Potential risks associated with 7-28 days of everolimus treatment include problems with wound healing and infections. Published data in patients with glioblastoma multiforme who underwent brain surgery, in a similar protocol to our study found no evidence of problems with wound healing or infection. There appears to increase the risk of infection and problems with wound healing in some patients who have received everolimus treatment and undergone organ transplantation but the risk of serious infection over control rates is not documented in patients with brain tumors or TSC.

For patients in the cardiac and renal transplant groups, much of the risk of infection and impaired wound healing is associated with obesity, age over 40 years old, and other factors. Further, the transplant groups in which wound healing issues have been identified suffer from chronic illness and treatment with other immunosuppressive agents. To reduce the potential risk to patients with TSC in our study, we will exclude patients who are 1) obese, 2) over age 50, 3) have a history of chronic medical illness, or 4) treatment with an immunosuppressant (other than everolimus during the 7-day trial). These criteria should minimize the potential for peri-operative infection or impaired wound healing. However, we will be vigilant with the Data Safety Monitoring Plan to closely assess all patients postoperatively and record all complications, including infection and impaired wound healing. Further, we will institute a special surveillance system to monitor for these potential side effects.

The following are possible benefits that could occur through this research study:

- 1) Elimination of need for epilepsy surgery if there is a significant reduction in seizure activity;
- 2) Improvement in seizure control, as well as reduction of cognitive, behavioral, and physical injury, and sudden death risks associated with ongoing seizures;
- 3) Improvement in cognitive or behavioral function; and
- 4) Reduction in signs and symptoms of TSC (e.g., renal angiomyolipomas, lymphangiomyomatosis, facial angiofibromas).
- 5) Close medical follow-up care

CONFIDENTIAL

This document and information is the property of the NYU School of Medicine and Langone Medical Center. Do not disclose or use except as authorized in writing by the study IND sponsor

For patients with FCD, the potential benefits are likely less, but could include 1 through 3 above since increased mTOR signaling is documented in FCD and it remains uncertain if Everolimus therapy may provide clinical benefits.

The potential risks of everolimus must be weighed against the potential benefits, which for the patients with TSC include: 1) elimination of need for epilepsy surgery if there is a significant reduction in seizure activity, 2) improvement in seizure control and reduction of cognitive, behavioral, physical injury, and sudden death risks associated with ongoing seizures, 3) improvement in cognitive or behavioral function, and 4) reduction in systemic signs and symptoms of TSC (e.g., renal angiomyolipomas, lymphangiomyomatosis, facial angiofibromas, etc.). For patients with FCD, the potential benefits are likely less, but could include 1 through 3 above since abnormalities of mTORC1 signaling are documented in FCD and it remains uncertain if therapy may provide clinical benefits.

## **2 Study Objectives**

### **2.1 Primary Objective:**

The primary objectives of this pilot study are to 1) test the feasibility and safety of recruiting patients into a prospective study before epilepsy surgery in patients with TRE and either TSC or FCD, and 2) test the hypothesis that everolimus therapy in TSC and FCD patients with TRE will reduce mTOR signaling (reduced S6 phosphorylation) as compared to TSC and FCD who did not receive everolimus (control group).

### **2.2 Secondary Objectives:**

The secondary objectives include

- 1) systemic mTOR signaling suppression (VEGF-D) pre-and post-treatment,
- 2) genetic analysis of resected brain tissue,
- 3) correlate blood everolimus levels with brain measures of S6 phosphorylation,
- 4) measure markers of cortical hyperexcitability (glutamate and GABA receptors, levels of neuroinflammation, axonal abnormalities, myelination defects) as compared to historical controls and
- 5) electrocorticographic (ECoG) recordings as compared to historical controls

## **3 Study Design**

### **3.1 General Design**

This is a multi center open-label pilot clinical trial of patients with TRE, ages 2 to 50 years old, with TSC or FCD who are scheduled for epilepsy surgery. Patients will be treated with everolimus for 7 to 21 days prior to epilepsy surgery with extension of time from 7 to 21 days in successive cohorts of patients. The initial cohort of at least three patients will be treated for 7 days and after the safety of therapy is assured for this group, there will be an extension of the treatment to 14 days for at least three patients. This will be extended at one week intervals/three patient groups to a maximum treatment duration of 21 days. Resected brain tissue will be analyzed for activation of mTORC1 and mTORC2 signaling pathways, glutamatergic and GABA-ergic neurotransmission using histochemistry, genetic analysis, as well as extracellular field recordings in acute ex-vivo brain slices from surgery. A blood sample, collected at the time of surgery, will be analyzed for everolimus levels and VEGF-D. All patients will undergo standardized intra-operative ECoG recordings over the primary epileptogenic region and reviewed blindly.

Subjects will be in the study for approximately 10 weeks. We will study variables listed in specific aims 1 and 2 in TSC and FCD patients treated with 7 to 21 days of everolimus and compare these to untreated control patients with TRE and TSC or FCD. A concurrent comparison group of 12 subjects will also be enrolled. They will all be undergoing routine surgery for the diagnosis of TRE with TSC or FCD.

All study procedures will be performed at either the Comprehensive Epilepsy Center (CEC) with the exception of the surgery, which will be performed at Tisch Hospital

CONFIDENTIAL

This document and information is the property of the NYU School of Medicine and Langone Medical Center. Do not disclose or use except as authorized in writing by the study IND sponsor

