## Study Summary

Title	A Pilot Study to Evaluate the Effects of Everolimus on Brain mTOR activity and Cortical Hyperexcitability in Tuberous Sclerosis Complex (TSC) and Focal Cortical Dysplasia (FCD)
Short Title	Everolimus effects on brain mTOR and excitability
Protocol Number	Pending
Phase	2
Methodology	This is a multi center, open-label exploratory Phase II clinical trial of patients with treatment resistant epilepsy (TRE), ages 2 to 50 years old, with TSC or FCD who are scheduled for epilepsy surgery.
Study Duration	18 months of active recruitment
Study Center(s)	NYU Langone Medical Center;
Objectives	
Primary objectives: A pilot study to assess the:
 
1) feasibility and safety of recruiting patients into a prospective study for patients with TSC and FCD treated for 7-21 days before epilepsy surgery and 2) test the hypothesis that everolimus therapy in TSC and FCD patients with TRE will reduce mTOR signaling (reduced S6 phosphorylation) as compared to concurrent controls with TSC and FCD who did not receive Everolimus.
 
Secondary Objectives: to obtain preliminary data on the effect of everolimus therapy in TSC and FCD patients with TRE on mTOR signaling and cortical hyperexcitability by assessing 1) systemic mTOR signaling suppression (VEGF-D) pre- and post-treatment, 2) relation of S6 phosphorylation to specific genetic abnormalities, and 3) blood everolimus levels; and using historical controls to assess 4) markers of cortical hyperexcitability (glutamate and GABA receptors, levels of neuroinflammation (TNF-<math>\alpha</math>), axonal abnormalities, myelination defects), and 5) electrocorticographic (ECOG) recordings

Number of Subjects	21 total subjects study wide; 9 treated subjects (NYU CEC) and 12 controls (@ NYU CEC;)  This has been a very challenging study to recruit for and therefore our total number of enrolled patients is fewer than expected. This has to do with multiple factors, including a smaller number of eligible candidates, a smaller percentage of parents who have considered to participate, and the challenge imposed by the fact that many of the patients come from outside the NY Tristate area. Given this distance, enrollment of subjects 3-4 weeks before the surgery has not been possible, so we have shortened the length of the treatment phase.

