### **3.3 Secondary Outcome Measures**

- Other mTOR downstream/upstream markers in the brain (S6 phosphorylation) and peripheral VEGF-D levels.
- Blood and brain levels of cytokines (and TNF- $\alpha$ ) and inflammatory proteins (HMGB1) at the time of surgery
- Brain glutamate and GABA receptor expression at the time of surgery
- Blood levels of everolimus at the time of surgery
- **Electrocorticography** of minimum of 10 minutes. Site of expected maximal epileptogenicity will be recorded with grid or strip array of at least 12 contact points. **Extracellular field and recordings in acute ex-vivo brain slice:** After resection, one brain sample will be immediately placed, under sterile **conditions, into cold, oxygenated artificial cerebrospinal fluid (ACSF)**. Tissue will be transported to the lab and, within 5-10 min from resection, acute brain slices will be prepared. Extracellular field recordings, from visually identified neurons will be employed to assess overall cortical excitability, intrinsic neuronal firing properties and basic synaptic function.

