## **4 Subject Selection and Withdrawal**

### **4.1 Inclusion Criteria (Active Group)**

1. Female and male patients, age 2 years to 50 years.
2. Diagnosis: treatment resistant epilepsy ( $\geq 2$  failed anti-epileptic drug [AED] treatment regimens) and either:
  - Tuberous Sclerosis Complex
  - Focal Cortical Dysplasia on MRI or neuropathology from prior brain surgery
3. Diagnosis of TSC confirmed by genetic testing and/or clinically definite diagnosis of TSC according to the modified Gomez criteria [31]. Clinically definite diagnosis is defined as:
  - Two Major Features, or
  - One Major Feature plus two Minor Features
4. Adequate bone marrow function as shown by: ANC  $\geq 1.5 \times 10^9/L$ , Platelets  $\geq 100 \times 10^9/L$ , Hb  $> 9$  g/dL;
5. Adequate liver function as shown by
  - a. Total serum bilirubin  $\leq 2.0$  mg/dL,
  - b. ALT and AST  $\leq 2.5 \times$  ULN ( $\leq 5 \times$  ULN in patients with liver metastases),
  - c. INR  $\leq 2$ ; if applicable
6. Adequate renal function: serum creatinine  $\leq 1.5 \times$  ULN;
7. Fasting serum cholesterol  $\leq 300$  mg/dL OR  $\leq 7.75$  mmol/L AND fasting triglycerides  $\leq 2.5 \times$  ULN. if applicable NOTE: In case one or both of these thresholds are exceeded, the patient can only be included after initiation of appropriate lipid lowering medication;
8. Signed informed consent obtained prior to any screening procedures.

CONFIDENTIAL

This document and information is the property of the NYU School of Medicine and Langone Medical Center. Do not disclose or use except as authorized in writing by the study IND sponsor

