As the majority of our surgical patients reside outside of the NYC area, there may be circumstances in which patients are unable to be present at the study site for consenting due to distance and travel issues. In such cases, the informed consent will be faxed or emailed to the patient. The principal investigator will then review and obtain consent over the phone. The principal investigator will explain the study in full detail and ensure that all questions are answered. The patient will then sign and date the informed consent and return it to the principal investigator via fax or email. Once received the principal investigator will sign and date the informed consent. A copy of this signed and dated informed consent will then be faxed or emailed to the patient before beginning any study procedures. The patient will also bring the original signed informed consent to the study site at the first visit to again be signed by the principal investigator. Both the mailed informed consent and the original will be kept on file and copies will be given to the patient. All phone correspondence and mailings will be documented in the study file. Telephone consent is necessary for these long distance subjects who will be coming in for a combined visit 1 and 2 as certain study procedures need to be completed prior to their combined visit. Particularly, in order to meet the inclusion criteria, patients who have not had certain bloodwork need to have it completed in order to be eligible for the study. Therefore, in certain cases we need to obtain consent prior to combined Visit 1 and 2 so that these patients can obtain bloodwork and confirm eligibility prior to this combined initial visit.

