## **6 Study Procedures**

### **5.7 Visit 1 (Active/Control Patients)**

**NOTE:** This visit will occur within 6 weeks of Visit 2, which will be when patient will be entered into the study.

CONFIDENTIAL

This document and information is the property of the NYU School of Medicine and Langone Medical Center. Do not disclose or use except as authorized in writing by the study IND sponsor

After Informed Consent is obtained and study consent form is signed, Study Visit 1 will include the following, from interaction with the subject, and/or as applicable the subject's parents or guardian:

- A detailed review of the research subject's medical records and interview to ensure that the subject meets inclusion criteria and does NOT meet any of the exclusionary criteria.
- History of current seizure types and frequencies, concomitant medical or psychiatric disorders, and all prescribed and over-the-counter medications taken.
- Complete review of systems.
- Subject physical examination, including recording of vital signs, including height and weight to compute body mass index (BMI; see above) and body surface area (BSA), and neurological examination.
- Subject will be instructed to begin a daily seizure diary today that will be maintained and collected at the next visit.

**5.8 Visit 2 – (Active patients- 'NOTE: This visit will occur 7-21 days before surgery; patients/caretakers will be given Everolimus. )**

The following activities will be conducted and research subject information will be collected by interaction with the subject, and/or as applicable the subject's parents or guardian:

- Recent history will be reviewed for any change in their medical status or change in intake of prescribed or over-the-counter medication.
- Vital signs, physical and neurological examination.
- Collect and review seizure diary kept since Visit 1 and give new diary to be recorded until date of surgery. The protocol for study medication administration will be reviewed with the subject, and/or parent/guardian as applicable.
- Explanation of potential adverse events will be reviewed, as will the reporting of adverse events.
- Blood work: CBC and C-reactive protein (CRP). If not done prior to visit as part of PST (pre surgical testing)
- Review of the specific protocol for medication administration. (Active Patients Only at NYU CEC)

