  - They will be instructed on the dosage and administration times of the study medication. All subjects will receive a specific quantity of tablets and they will be asked to record the time that each dose is given. They will be asked to bring back the medication that was not used so it can be reconciled with expected number of tablets to be used. This reconciliation will be logged on the drug reconciliation form, and signed and dated by the study team

6.2a Visit 2a – For patients taking the Everolimus for 3 weeks, at NYU CEC, they will have serum levels of everolimus drawn after 10-12 days on the medication. A trough level will be obtained. The study nurse or doctor will contact the patient with the results when available and will adjust the dose as described above. The nurse or doctor will also ask the patient to report any adverse events.

For active patients who reside outside of the NYC area and are unable to arrive at NYU CEC due to distance and travel issues prior to pre-admission testing, Visits 1 and 2 will be combined as one visit to be completed at least 7 days prior to Visit 3. For these patients with a combined Visit 1 and 2, this could mean a treatment window of 7-21 days depending both on which cohort they are in and how soon they can begin treatment.

Pre-surgical evaluation: Visit 2- Control Group

- Recent history will be reviewed for any change in medical status or change in intake of prescribed or over-the-counter medication.

CONFIDENTIAL

This document and information is the property of the NYU School of Medicine and Langone Medical Center. Do not disclose or use except as authorized in writing by the study IND sponsor

- Vital signs, physical and neurological examination
- A detailed seizure history during the prior week.
- Medication reconciliation.

Blood work: (pre surgical eval) CBC and C-reactive protein(CRP).

For control patients who reside outside of the NYC area and are unable to arrive at the study site due to distance and travel issues prior to pre-admission testing, Visits 1 and 2 will be combined as one visit and can be completed one day prior to Visit 3 if not earlier.

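### VEGF-D is promised before and after treatment, but the stated schedule times a VEGF-D sample only at surgery and names no paired analysis, so the within-patient change cannot be computed from it

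*Combined protocol and SAP*

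**What the plan says.** The Study Summary lists as its first secondary item "systemic mTOR signaling suppression (VEGF-D) pre- and post-treatment". Section 2.2 repeats it: "systemic mTOR signaling suppression (VEGF-D) pre-and post-treatment". Section 3.3 includes "and peripheral VEGF-D levels" among the secondary outcomes, without a time point.

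Section 3.1 gives the one sampling time: "A blood sample, collected at the time of surgery, will be analyzed for everolimus levels and VEGF-D". It does not say whether this applies to treated patients only or to both groups.

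The active-group Visit 2 list, the visit at which drug is handed out, has "Blood work: CBC and C-reactive protein (CRP", to be done then unless pre-surgical testing has already covered it. The control-group Visit 2 list has "Blood work: (pre surgical eval) CBC and C-reactive protein(CRP". Visit 3 is headed for active and control patients. Its research-blood item names everolimus level, cytokines and a measure of mTOR activity, does not name VEGF-D, and sits under a sub-heading restricted to active patients.

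Section 6.1 plans descriptive summaries by cohort and group, a two-sample t-test of treated against comparison patients for S6 phosphorylation, similar analyses for the other continuous endpoints, and scatterplots with correlations between endpoints.

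**The concern.** A before-and-after objective needs a sample before the first dose and an analysis that uses each patient's own baseline. The schedule states neither. A missing analysis can be written later, but a missing pre-dose sample cannot be recovered once the patient has taken everolimus.

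Without the baseline, the most that VEGF-D can offer is a contrast between treated and control patients on the day of surgery. Under section 5.4 patients choose their group, and those who decline treatment are asked to be controls. Section 4.1.1 matches on age, sex and diagnosis, which helps but does not remove self-selection. A surgery-day contrast therefore cannot separate a drug effect from a VEGF-D difference that was already there. Even that contrast needs control blood, which the text does not clearly provide for.

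**Working it through.** The plan gives no sample size, power, variance or expected effect for VEGF-D, so there is no figure to reproduce. The check is to set the objective against every blood draw described.

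1. **Visit 1:** no blood draw is listed.
2. **Visit 2, active patients:** blood count and CRP. No VEGF-D and no stored sample.
3. **Visit 2, controls:** blood count and CRP.
4. **Visit 2a:** everolimus trough after 10 to 12 days on drug, three-week patients only. This is not a baseline.
5. **Surveillance blood (section 6.5, Medical Monitoring):** one draw falls 7 to 10 days before everolimus starts, but its content is a blood count with differential and CRP.
6. **Eligibility blood (sections 4.1 and 4.3):** needed for the entry criteria; VEGF-D is not mentioned.
7. **Visit 3:** research blood, stored frozen, with VEGF-D not named. The last everolimus dose is taken that morning, so a sample at surgery can serve as the on-treatment value but not as the baseline.
8. **Research assays under Visit 5a:** DNA, mTOR proteins in lymphocytes, inflammatory markers and microRNA. VEGF-D is not mentioned.

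Count per treated patient:
- VEGF-D samples with a stated draw time: 1 (surgery, section 3.1).
- Stated pre-dose VEGF-D samples: 0.
- Computable within-patient changes: 0 of 9. With a pre-dose tube added for everyone: up to 9 of 9.

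Analysis: section 6.1 contains descriptive summaries, a between-group test and correlations. None of these is a change from baseline.

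For context, the precision that the pairs would give. The half-width of a 95% confidence interval for the mean change, in units of the standard deviation (SD) of the change, is t(0.975, n−1)/√n:
- n = 9: 2.306/3 = 0.77
- n = 6: 2.571/2.449 = 1.05
- n = 4: 3.182/2 = 1.59

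The smaller values of n illustrate the case in which some patients were dosed before a tube was added. The documents do not say how many that would be.

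**The case against.** The strongest reply is that the baseline is implied. Two places state the before-and-after intent, and section 3.3 ties cytokines, receptors and everolimus levels to surgery but leaves VEGF-D without a time. The visit lists are also plainly incomplete. Section 4.1 requires blood-based criteria such as "Adequate liver function as shown by", section 4.3 says that "patients who have not had certain bloodwork need to have it completed in order to be eligible for the study", and Visit 5a relies on blood DNA, yet no visit lists those tubes. Silence in such lists is weak evidence that no baseline is drawn.

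This stands as far as it goes. A reader might infer that no baseline is or will be taken, and the documents do not support that. They show only that staff who follow the written schedule would not take one.

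Two other strong readings also fail. A reader might infer that the analysis plan holds nothing but a between-group t-test; it also plans descriptive summaries and correlations, and lacks only the paired analysis. A reader might also take the surgery-day comparison with controls as a secure fallback and calculate how far self-selection distorts it. The control sample is not clearly specified. Any such error rate would rest on assumed baseline differences and would apply to every endpoint in this 9 versus 12 design.

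Finally, this is a secondary marker in a pilot that claims no power for it. That limits the severity, but it does not reconcile the objective with the schedule.

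**Conclusion.** The objective and the schedule do not agree. As written, 0 of 9 treated patients have a specified before-and-after VEGF-D pair, no paired analysis is named, and whose blood is assayed at surgery is unclear. The point deserves correction because a missed baseline is permanent and the remedy is small. It does not threaten the primary objectives.

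The count of 0 of 9 comes from the documents and needs no assumed value. It concerns the stated schedule, not actual conduct. It also covers only the text available for review: a part of the document between the sample-size paragraph and the safety reporting section was not available. If a pre-dose VEGF-D draw is set out there, the sampling part of the point falls.

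**What to change.** 1. **Sampling.** Add one stored VEGF-D tube before the first dose for active patients, at Visit 2 or at the combined Visit 1 and 2. Name VEGF-D in the Visit 3 research sample and state that it is drawn in both groups. If a baseline tube is already intended, list it in the visit schedule.
2. **Analysis.** Add to section 6.1 a within-patient summary of VEGF-D in treated patients who have both samples: the paired change with a confidence interval. Report it alongside the treated-versus-control comparison at surgery. State that the change has no control over a matched interval: the combined control visit may fall one day before surgery, whereas active patients start 7 to 21 days before.
3. **If no baseline will be taken, or for patients already dosed without one.** Reword the Study Summary and section 2.2 as a comparison at surgery. This works only if the control draw in step 1 is made. The Study Summary describes recruitment as already under way, so the number of patients without a baseline should be established and reported.

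Cost: one extra tube and one extra assay per treated patient, plus the surgery-day control sample and assay if not already planned. Patients whose blood count and CRP were done earlier as pre-surgical testing would need a separate draw, which matters most in young children. Rewording the objective costs only text once the control sample is secured.
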